**Table CXAD.6.2. Rules for Determining Date of Progression or Censor for Progression-Free Survival**

Rule	Situation	Date of Progression or Censor	Outcome
1	No baseline tumor assessments	Date of first treatment	Censored
2	No postbaseline assessments and no death	Date of first treatment	Censored
3	No documented progression and no death (with a postbaseline tumor assessment)	Date of last adequate tumor assessment	Censored
4	Patient lost to follow-up (or withdrew consent from study participation) before documented progression or death	Date of last adequate tumor assessment	Censored
5	Documented progression	Date of documented progression  If a tumor assessment was done on multiple days, use the earliest date for that visit.	Progressed
6	Death without documented progression	Date of death	Progressed
7	Documented progression or death after missing $\geq 2$ consecutive postbaseline tumor assessments	Date of last adequate tumor assessment before missed assessments or date of first treatment, whichever is later	Censored

Note: Progression-free survival and associated outcome is determined by the earliest of the dates above, if more than 1 situation applies.

### **6.13.2. Efficacy Analysis Variables (RECIST v1.1 with confirmatory scan for disease progression)**

For Study CXAD, RECIST v1.1 with confirmatory scan for disease progression (denote it as RECISTc for simplicity) will be adapted to account for the unique tumor response characteristics seen with treatment of immuno-oncology therapy. RECISTc will be applied as detailed in the study protocol, and the resulting data will be included in the clinical database.

**Objective response rate (RECISTc)** is defined as the proportion of treated patients achieving a best overall response of PR or CR per RECISTc. Particularly, the best overall response by RECISTc (denoted as ORRc) closely related to confirmed response by RECIST v1.1. ORRc further captures responses after unconfirmed PD and it does not require confirmation. For example:

- If the best response by RECIST is CR, then the best response by RECISTc is CR.
- If the best response by RECIST is PR, SD, or PD, the best response by RECISTc is the best response over the initial assessment (prior to PD by RECISTc) and the confirmation stage.

Overall, the best response by RECISTc should be the same or better than the best response by RECIST criteria. In addition, patients who do not have any postbaseline tumor response

assessments for any reason are considered non-evaluable and will be included in the denominator when calculating the response rate.

[figure not shown]
**PFSc:** The date from the treatment started date to the time of confirmed PD (PDc) assessed by RECISTc.

- If the initial PD is confirmed at the very next scan (consecutive PD) then the date of PDc is the initial PD date by RECIST v1.1.
- If the initial PD is unconfirmed at the very next scan (non-consecutive PD), then the date of PDc is the date of second PD.

[figure not shown]
**Duration of response by RECISTc:** The duration of response is defined from the date measurement criteria for CR or PR (whichever is first recorded) are first met to the date of PDc or the date of death due to any cause, in the absence of an observed PDc.

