Table CXAD.8.2 provides an overall comparison across the 2 measures of disease progression to be used in Study CXAD, and irRC.

Table CXAD.8.2. Summary of Response Assessment by RECIST, RECIST with Confirmatory Scan for Progressive Disease, and irRC

Definition	Used in Study CXAD		Not Used in Study CXAD
	RECIST v1.1	RECIST v1.1 with confirmatory scan for PD	irRC (Wolchok et al. 2009)
New lesion	The presence of new lesion defines progression	The presence of new lesion defines progression	The presence of new lesion does not define progression The measurements of the new lesion(s) are included in the sum of the measurements
Confirmation of PD	Not required	PD, in the absence of clinically significant deterioration, requires confirmation with repeat imaging after ≥ 4 weeks. After initial PD following RECIST v1.1, shift to “RECIST v1.1 with confirmatory scan for PD.”	Required

Abbreviations: irRC = immune-related response criteria; progressive disease = PD; RECIST = Response Evaluation Criteria in Solid Tumors.

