10.9. Efficacy

Tumor response data will be provided by cohort/expansion arm (according to RECIST v1.1). Particularly, the antitumor effect will be summarized by best overall response, including the overall response rate (ORR) and disease control rate (DCR). A patient is considered to have a tumor response if they achieve a confirmed CR or PR. The ORR will be estimated by dividing the total number of confirmed complete and partial responders (CR+PR) by the total number of enrolled patients. The DCR will be estimated by dividing the total number of CR+PR+SD by the total number of enrolled patients. A 95% exact CI will be constructed to determine the level of precision of the ORR and DCR. Time-to-event variables such as PFS, time to response, duration of response and overall survival will be tabulated, and the Kaplan-Meier method (Kaplan and Meier 1958) will be used to estimate the survival curves, medians, and survival rates (eg, 6-month survival rate) if applicable.

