PD: At least a 20% increase in the sum of the diameters of target lesions, taking as reference the smallest sum on study (including the baseline sum if that is the smallest). In addition to the relative increase of 20%, the sum must also demonstrate an absolute increase of at least 5 mm. The appearance of 1 or more new lesions is also considered progression.

For equivocal findings of progression (for example, very small and uncertain new lesions; cystic changes or necrosis in existing lesions), treatment may continue until the next scheduled assessment. If at the next scheduled assessment, progression is confirmed, the date of progression should be the earlier date when progression was suspected.

SD: Neither sufficient shrinkage to qualify for PR, nor sufficient increase to qualify for PD, taking as reference the smallest sum diameters while on study.

Not Evaluable: When an incomplete radiologic assessment of target lesions is performed or there is a change in the method of measurement from baseline that impacts the ability to make a reliable evaluation of response.

Evaluation of Nontarget Lesions

Complete Response (CR): Disappearance of all nontarget lesions and normalization of tumor marker level. All lymph nodes must be nonpathological or normal in size (<10-mm short axis).

Non-CR/Non-PD: Persistence of 1 or more nontarget lesions and/or maintenance of tumor marker level above the normal limits.

PD: Unequivocal progression of existing nontarget lesions. The appearance of 1 or more new lesions is also considered progression.

Not Evaluable: When a change in method of measurement from baseline occurs and impacts the ability to make a reliable evaluation of response.

Evaluation of Best Overall Response

The best overall response is the best response recorded from the start of the study treatment until the earliest of objective progression or start of new anticancer therapy, taking into account any requirement for confirmation. The patient's best overall response assignment will depend on the findings of both target and nontarget disease and will also take into consideration the appearance of new lesions. The best overall response will be calculated via an algorithm using the assessment responses provided by the investigator over the course of the trial.

Time Point Response

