The main goal of confirmation of objective response in clinical trials is to avoid overestimating the response rate observed. The confirmation of response is particularly important in *nonrandomized trials* where response (CR/PR) is the primary end point. In this setting, to be assigned a status of PR/CR, changes in tumor measurements must be confirmed by repeat assessments that should be performed no less than 4 weeks after the criteria for response are first met. To confirm a response of CR, a full assessment of all target and nontarget lesions that were present at baseline must occur, including those measured by bone scan. To confirm a PR or SD, a full assessment of target lesions that were present at baseline must occur; assessment of nontarget lesions is not required.

However, in *randomized trial* (Phase 2 or 3) or studies where SD or progression is the primary endpoints, confirmation of response is not required. But, elimination of the requirement may increase the importance of central review to protect against bias, in particular of studies which are not blinded.

In the case of SD, follow-up measurements must have met the SD criteria at least once after start of treatment at a minimum interval not less than 6 weeks measured from first dose.

Duration of Overall Response

The duration of overall response is measured from the time measurement criteria are first met for CR or PR (whichever is first recorded) until the first date that disease is recurrent or objective progression is observed (taking as reference for PD the smallest measurements recorded on study).

The duration of overall CR is measured from the time measurement criteria are first met for CR until the first date that recurrent disease is objectively documented.

Duration of Stable Disease

Stable disease is measured from the start of the treatment (in randomized trials, from date of randomization) until the criteria for objective progression are met, taking as reference the smallest sum on study (if the baseline sum is the smallest, that is the reference for calculation of PD).

Independent Review of Response and Progression

When objective response (CR + PR) is the primary end point, and when key drug development decisions are based on the observation of a minimum number of responders, it is recommended that all claimed responses be reviewed by an expert(s) independent of the study. If the study is a randomized trial, ideally reviewers should be blinded to treatment assignment.

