#### **6.13.1. Efficacy Analysis Variables (RECIST v.1.1)**

Definition of efficacy analysis variables are listed alphabetically.

**Disease Control Rate** is defined as the proportion of treated patients achieving a best overall response of complete response (CR), partial response (PR), or stable disease (SD) per RECIST v.1.1. Patients who do not have any postbaseline tumor response assessments for any reason are considered non-responders and are included in the denominator when calculating the response rate.

**Note.** Best overall response is the best response recorded from the start of treatment until disease progression, in the order of CR, PR, SD, PD, and NE.

**Duration of Response** is defined from the date of first documented CR or PR that is subsequently confirmed (responder) to the date of objective progression or the date of death due to any cause, whichever is earlier. If a responder is not known to have died or have objective progression, then the patient will be censored at the date of last evaluable tumor assessment.

**Objective response rate** is defined as the proportion of treated patients achieving a best overall response of PR or CR per RECIST v.1.1. Patients who do not have any postbaseline tumor response assessments for any reason are considered non-evaluable and are included in the denominator when calculating the response rate.

**Overall survival** is defined as time from the date of first treatment to the date of death from any cause. For each patient who is not known to have died as of the data-inclusion cut-off date for a particular analysis, OS will be censored for that analysis at the date of last contact prior to the data-inclusion cut-off date (contacts considered in the determination of last contact date include AE date, lesion assessment date, visit date, and last known alive date).

**Progression-free survival** is defined as the time from the date of first treatment until the date of radiographic documentation of progression (as defined by RECIST v. 1.1) based on investigator assessment or the date of death due to any cause, whichever is earlier.

**Time-to-response** is the time from the date of first study treatment until the first evidence of a confirmed CR or PR.

[Table CXAD.6.2](#) lists rules for determining date of progression or censor for PFS. The censoring is taken in the following order:

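### SAP 6.13.2 waives confirmation of response for ORRc and the best-overall-response note in SAP 6.13.1 omits it, whereas Protocol 10.9 counts only confirmed CR or PR

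*SAP*

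**What the plan says.** **Protocol.** Section 10.9 gives the rule: "A patient is considered to have a tumor response if they achieve a confirmed CR or PR". The ORR is obtained by "dividing the total number of confirmed complete and partial responders (CR+PR) by the total number of enrolled patients". Attachment 10 runs best overall response "until the earliest of objective progression or start of new anticancer therapy, taking into account any requirement for confirmation", and confirmation means "repeat assessments that should be performed no less than 4 weeks after the criteria for response are first met".

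Section 8.3.1 and Table CXAD.8.2 add one thing to standard RECIST v1.1. When there is no clinically significant deterioration, a first progression has to be confirmed by a repeat scan at least 4 weeks later. Neither place relaxes confirmation of response. Section 8.3.1.2 itself still speaks of a confirmed CR or PR when it sets out this version.

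**SAP 6.13.1 (RECIST v1.1).** The note reads: "Best overall response is the best response recorded from the start of treatment until disease progression", followed by the ranking of categories. ORR is the share of treated patients whose best overall response is CR or PR. Neither the note nor the ORR definition mentions confirmation. In the same section, duration of response and time to response both start from a CR or PR that is confirmed.

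**SAP 6.13.2 (RECISTc).** RECISTc is to be applied as the protocol sets out, yet "ORRc further captures responses after unconfirmed PD and it does not require confirmation". Best response is taken over the initial stage and the confirmation stage. RECISTc duration of response starts when the criteria are first met, with no mention of confirmation. Scenario 1 of the graphic example says that when the initial PD is confirmed at the next scan, the RECISTc and RECIST variables coincide.

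**The concern.** The SAP states a rule for ORRc that the protocol does not contain, in the same subsection that says RECISTc follows the protocol. The v1.1 ORR rests on a note that leaves out a condition which Protocol 10.9 makes part of the definition of response. A programmer working from the SAP alone could build either version of the v1.1 ORR and would build an unconfirmed ORRc.

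Response is the main read-out of antitumor activity in two expansion arms of about 15 patients without a control. Dropping confirmation can only leave the rate unchanged or raise it. The responder sets may also stop matching: a patient could count in the ORR and have no duration of response or time to response.

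**Working it through.** **1. Is the difference in the numerator or the denominator?** The protocol divides by enrolled patients and the SAP by treated patients. Both documents define enrolled as having received at least one dose, so the denominators agree. The difference lies in the numerator.

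**2. One patient followed through each rule.** Take PR at the first scan, PD at the second and PD at the third. The PR is never confirmed, and the initial PD is confirmed at the next scan, so Scenario 1 applies.

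| Rule | Responder? | Consequence |
|---|---|---|
| Protocol 10.9 | No | PR not confirmed |
| SAP 6.13.1 read literally | Yes | Conflicts with Protocol 10.9; no duration of response or time to response under 6.13.1 |
| SAP 6.13.1 read as confirmed | No | Agrees with Protocol 10.9 |
| SAP 6.13.2 (ORRc) | Yes | PR is the best response before PD by RECISTc, and confirmation is waived |

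If the v1.1 ORR is literal, Scenario 1 holds but Protocol 10.9 is breached. If the v1.1 ORR is confirmed, Protocol 10.9 holds but Scenario 1 fails: this patient is in ORRc and not in ORR, for a reason unrelated to response after an unconfirmed progression. No reading satisfies Protocol 10.9, the ORRc waiver and Scenario 1 together.

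**3. The plan's own figures.** Exact (Clopper-Pearson) limits for x responders among n = 15 are the 0.025 quantile of Beta(x, n − x + 1) and the 0.975 quantile of Beta(x + 1, n − x), with a lower limit of 0 when x = 0. They reproduce the table in Protocol 10.1 and SAP 5.1 after rounding: 0/15, 0 to 0.218; 3/15, 0.043 to 0.481; 6/15, 0.163 to 0.677; 9/15, 0.323 to 0.837.

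**4. Size per patient.** One patient is 1/15 = 6.7 percentage points.

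| Counted responders | Rate | Exact 95% CI |
|---|---|---|
| 0/15 | 0% | 0 to 21.8% |
| 1/15 | 6.7% | 0.2 to 31.9% |
| 2/15 | 13.3% | 1.7 to 40.5% |
| 3/15 | 20.0% | 4.3 to 48.1% |

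For example, 3/15 without confirmation becomes 2/15 if one of the three is not confirmed, and 1/15 if two are not.

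**5. How often.** The documents give no rate of failed confirmation. Let q be the assumed share of patients with a CR or PR that is never confirmed. The chance that at least one enters the rate of a 15-patient arm is 1 − (1 − q)^15, and the expected number is 15q.

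| Assumed q | Chance of at least one | Expected number |
|---|---|---|
| 2% | 26% | 0.3 |
| 5% | 54% | 0.75 |
| 10% | 79% | 1.5 |
| 15% | 91% | 2.25 |

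**The case against.** **Confirmation was probably meant for the v1.1 ORR.** SAP 6.13.1 defines ORR by reference to RECIST v1.1 and equates a responder with a CR or PR that is later confirmed. SAP 6.13.2 speaks of confirmed response under v1.1, and Protocol 10.9 is explicit. This stands. A reader might infer that single-scan shrinkage definitely enters the v1.1 ORR; the documents show only an omission. The same limit applies to responders without a duration of response.

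**The two complaints cannot both be made.** A reader might say that the v1.1 ORR is unconfirmed and also that ORRc minus ORR is contaminated by ordinary unconfirmed PRs. If both rates are unconfirmed, those PRs appear in both and cancel. Contamination arises only if the v1.1 ORR is confirmed. This stands too, so the point is put as two alternatives.

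**ORRc is an addition, openly described.** Protocol 10.9 defines no ORRc, and the v1.1 rate is reported as well. That is why labelling it would be enough. It does not remove the conflict with the SAP's own statement that RECISTc follows the protocol.

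**Attachment 10 stresses confirmation where response is the primary endpoint of a nonrandomized trial.** Response is secondary here, but Protocol 10.9 applies confirmation expressly.

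**The missing stop at new anticancer therapy.** Attachment 10 ends the window there and the SAP note does not. A reader might infer that this inflates the ORR. It does not cause single-scan counting, and Protocol 6.2 and 8.1.2.2.3 stop scheduled tumor assessments once new therapy starts, so few later scans would exist.

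**Two scans for progression, one for response.** As a general statement this goes too far, because progression needs confirmation only when there is no clinically significant deterioration.

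**Conclusion.** The inconsistency is real. For ORRc it is a stated rule that conflicts with the protocol; for the v1.1 ORR it is an omission that one sentence would close. Whichever way SAP 6.13.1 is read, something in the two documents gives way: Protocol 10.9 on the literal reading, Scenario 1 on the confirmed reading.

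The direction is certain, since an unconfirmed rate cannot be below the confirmed one. The size is 6.7 points per patient in an arm of 15, and how many patients are affected is an assumption. The intervals in question overlap widely. A reader might infer that trial decisions are at risk, but the documents do not support that: analyses are descriptive without p-values, response is secondary, and the example rates are expressly not decision criteria. No alpha, power or sample size changes. The SAP should be corrected so that the reported rates mean what Protocol 10.9 says they mean.

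**What to change.** - **SAP 6.13.1:** state that a best overall response of CR or PR requires confirmation at least 4 weeks after the criteria are first met, as in Protocol 10.9 and Attachment 10.
- **SAP 6.13.2:** apply the same confirmation to CR or PR before and after an unconfirmed PD, and restrict RECISTc duration of response to those confirmed responders. Alternatively, keep the unconfirmed ORRc, label it exploratory and report it beside a confirmed rate.
- **Scenario 1:** check that it still holds under the option chosen, and reword it if not.
- **Minor alignment:** end the best-overall-response window at the earlier of objective progression and the start of new anticancer therapy, as in Attachment 10. Little effect is expected.

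The cost is SAP wording and a small change to the response algorithm. Scheduled scans about 8 weeks apart already satisfy the 4-week interval, so the schedule needs no additions. ORR and ORRc may be slightly lower, and a patient who leaves before a second scan would not count. Listing unconfirmed responses separately keeps that information.

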**Graphic Example:**

Scenario 1: The initial PD is confirmed at the next scan (consecutive PD). The efficacy variables by RECISTc and RECIST are the same.

Scenario 2: The initial PD is not confirmed at the next scan (non-consecutive PD). The efficacy variables by RECISTc and RECIST are different.

In addition, the best response after initial PD may be listed. Other efficacy analysis based on RECIST and/or RECISTc may be performed for exploratory analysis (e.g., in patients who had baseline and at least one post-baseline scan).

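### SAP 6.13.2 defines PFSc as time to confirmed PD and leaves out death, and the PFS event and censoring table is neither extended to it nor usable unchanged

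*SAP*

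**What the plan says.** **RECIST v1.1 PFS.** SAP 6.13.1 runs PFS from first treatment to radiographic progression "based on investigator assessment or the date of death due to any cause, whichever is earlier". It adds that Table CXAD.6.2 "lists rules for determining date of progression or censor for PFS". Rule 6 of that table, "Death without documented progression", is an event on the date of death. Rule 5 takes documented progression as the event. A note under the table applies the earliest date when several situations fit.

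**PFSc.** SAP 6.13.2 gives "The date from the treatment started date to the time of confirmed PD" (PDc). It names neither death nor censoring and does not mention the table. Two bullets date PDc. If the next scan confirms the initial PD, PDc takes the initial date. The other bullet begins "If the initial PD is unconfirmed at the very next scan (non-consecutive PD") and uses the date of the second PD.

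**RECISTc duration of response.** The next definition in the same section ends at PDc or at "the date of death due to any cause, in the absence of an observed" PDc.

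**Scenarios and link to the protocol.** The Graphic Example opens "Scenario 1: The initial PD is confirmed at the next scan (consecutive PD") and states that the RECIST and RECISTc variables then coincide; they differ when the initial PD is not confirmed. SAP 6.13.2 also states that "RECISTc will be applied as detailed in the study protocol". Protocol Table CXAD.8.2 and Section 8.3.1.2 require confirmation of PD only when there is no clinically significant deterioration. Protocol 10.9 lists PFS and does not define PFSc.

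**The concern.** The drafters included death in one RECISTc time-to-event variable and left it out of the one beside it, while keeping the PFS name. SAP 6.13 plans Kaplan-Meier estimation for all time-to-event variables, so every patient needs an event date or a censoring date. A programmer working from 6.13.2 has neither for a patient who dies before confirmed PD.

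What is at stake is the comparison of PFSc with PFS. The SAP presents the difference as a matter of how PD is confirmed and dated. Under the literal text, part of any gap could be uncounted deaths, which a reader could mistake for benefit after an unconfirmed first PD. Antitumor activity is a secondary objective.

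**Working it through.** The documents state no sample size, event count or rate for PFS or PFSc, so there is no plan figure to reproduce. The check has two parts.

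**1. Applying the definitions to hypothetical histories.** The days are invented, on the 8-week scan spacing in protocol 8.1.

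| History | PFSc as written | Table CXAD.6.2 unchanged | Death counted, table read with PDc |
|---|---|---|---|
| A. PD day 56, PD day 112 | event day 56 | event day 56 (rule 5) | event day 56 |
| B. PD day 56, SD day 112, PD day 168 | event day 168 | event day 56 (rule 5) | event day 168 |
| C. SD day 56, death day 80 | no event, no censoring date | event day 80 (rule 6) | event day 80 |
| D. PD day 56, death day 75, no second scan | no PDc, outcome undefined | event day 56 (rule 5) | event day 75, unless a deterioration rule makes day 56 PDc |
| E. PD day 56, SD day 112, alive at cutoff | no event, no censoring date | event day 56 (rule 5) | censored day 112 (rule 3) |

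The unchanged table agrees with the PFSc text only in history A. In B and E, rule 5 with the earliest-date note turns PFSc back into RECIST v1.1 PFS. In C, it supplies an event that the PFSc definition does not contain. So the table is not silently incorporated: it has to be rewritten with PDc in place of documented progression. With that substitution, and death counted, histories A, B, C and E resolve.

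Three matters remain after the substitution:

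- **Initial PD with clinically significant deterioration** (a possible form of D). The protocol requires no confirmation, but both PDc bullets presuppose a next scan. The SAP states neither the event status nor the date.
- **Alive after an initial PD with no further adequate scan.** SAP 6.13.1 counts a PD scan as adequate, so rules 3 and 4 would censor at the scan that showed PD. That is a convention, and possibly an informative one, so it should be chosen deliberately.
- **Rule 7 against backdating.** Take PD at week 8, two missed scans, then PD at the next scan performed. The first PDc bullet gives an event at week 8; rule 7 could give censoring at week 8.

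**2. Direction and illustrative size.** For any one patient, time to PDc cannot be shorter than time to PDc or death. If deaths are censored at the date of death, the Kaplan-Meier curve that ignores them is nowhere lower.

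Take an arm of 15 (the planned expansion arm size). Suppose k patients die before the first postbaseline scan, which falls at about week 8 (protocol Attachment 1, before Cycle 3). The other 15 − k have the same outcomes on both measures, with curve S(t). The value of k is assumed.

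- Deaths counted: PFS(t) = (15 − k)/15 × S(t) from the last of these deaths onward.
- Deaths censored: PFSc(t) = S(t). Censoring at day 1 or at death gives the same result, because no PD precedes the first scan.
- Ratio PFS/PFSc = (15 − k)/15: k = 1, 14/15 = 0.933; k = 2, 13/15 = 0.867; k = 3, 12/15 = 0.800; k = 0, 1.

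Example with k = 2 and confirmed PDs of 5, 4 and 2 patients at weeks 8, 16 and 24:

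- Week 8: 8/15 = 53.3% v 8/13 = 61.5%.
- Week 16: 4/15 = 26.7% v 4/13 = 30.8%.
- Week 24: 2/15 = 13.3% v 2/13 = 15.4%.

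The absolute gap shrinks as the curve falls. Just before the first scan it is 6.7 points per death (k = 1: 93.3% v 100%). Where PFSc is 30%, it is 2.0 points per death (28.0%, 26.0% and 24.0% for k = 1, 2 and 3). The formula covers only deaths before the first scan. Later deaths without PDc would also go uncounted, but their effect depends on timing that the documents do not give.

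**The case against.** The strongest reply is that this is a slip of wording. The endpoint keeps the name progression-free survival, 6.13.1 has just defined that as PD or death, and the Graphic Example describes only a difference in PD confirmation. On that reading death is counted and the numerical effect is zero. I accept that an omission is the likelier explanation. It does not remove the point: the adjacent duration-of-response definition names death, the PFSc sentence does not, and the table that might fill the gap contradicts the PFSc dating bullets.

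Other parts of the reply narrow the point and stand:

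- A reader might infer separate gaps for loss to follow-up and data cutoff. The documents do not support that: once PDc is substituted, rules 3 and 4 censor at the last adequate assessment.
- A reader might infer that PFSc lacks a rule for new anticancer therapy. Table CXAD.6.2 has none for RECIST v1.1 PFS either, so this is not a PFSc defect.
- The status of PD with deterioration is arguably carried in by the SAP's reference to the protocol, so the clearest omission there is the date. Protocol 6.2 also continues scans for patients who stop treatment for reasons other than progression, so cases without a further scan should be fewer.
- Protocol entry requires an estimated life expectancy of at least 12 weeks, which may limit deaths before week 8, although it is only an estimate.
- Some figures in 6.13.2 are not shown. The point rests on the written definition.

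**Conclusion.** The point holds as a wrong stated definition that should be corrected. As written, PFSc is time to confirmed progression labelled PFS, and the PFS table neither extends to it nor can apply to it unchanged.

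A reader might go further and infer that reported PFSc will be materially inflated. The documents do not support this. They give no rate of death before PDc, and the factors of 0.933 to 0.800 depend on an assumed 1 to 3 deaths among 15 before the first scan. With no such deaths, or if the sponsor already means to count death, there is no difference.

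Nor does the issue threaten the trial's conclusions. SAP 6.1 makes all analyses descriptive without p-values, PFSc appears only in the SAP and drives no decision, and RECIST v1.1 PFS and OS are unaffected.

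**What to change.** In SAP 6.13.2, replace the definition with: *PFSc is the time from first treatment to PDc or death from any cause, whichever is earlier; Table CXAD.6.2 applies with PDc in place of documented progression.* If death is deliberately excluded, rename the endpoint time to confirmed progression and give it its own censoring rules.

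In the same edit, state:

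- the event status and date for an initial PD with clinically significant deterioration, consistent with protocol Table CXAD.8.2 and Section 8.3.1.2;
- the convention (event or censoring, and the date) for a living patient with an initial PD and no further adequate scan;
- whether rule 7 or the backdating of PDc takes precedence when two or more scans are missed between the initial and confirming PD.

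Counting death and substituting PDc costs SAP wording and derivation code. The deterioration rule may need more: the protocol's study schedule lists no item recording clinically significant deterioration, so the sponsor should check that the case report form captures it. PFSc estimates would become less favourable only if deaths before PDc occur and would otherwise have gone uncounted.
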